### 2.5. Justification for Strength of Ruxolitinib Cream

Results from Study INCB 18424-211 showed that ruxolitinib 1.5% cream BID had the highest repigmentation rate on both F-VASI and T-VASI, particularly at Week 48. All ruxolitinib treatment strengths were generally safe and well tolerated with no significant TEAEs or application site events and no clinically relevant hematological changes. Also, the available data for phototherapy combination was with ruxolitinib 1.5% cream BID. Further, in the 2 Phase 3 studies, ruxolitinib 1.5% BID showed statistically significant and clinically meaningful improvements for F-VASI and T-VASI compared with vehicle, and the safety profile was similar to that seen in the Phase 2 study.

### 2.6. Justification for Dose of Narrow-Band Ultraviolet B Phototherapy

NB-UVB phototherapy is an established treatment modality for vitiligo. Recent research suggests that in addition to an immunosuppression effect, NB-UVB stimulates growth and migration of remaining perilesional and follicular melanocytes. A combination of NB-UVB and ruxolitinib cream may lead to an accelerated rate of repigmentation, and potentially a more durable response to treatment.

NB-UVB phototherapy administered 3 times per week (see Table 7) has been chosen as the regimen for this study as this regimen has been shown to induce repigmentation (Mohammad et al 2017); therefore, starting at Week 12 participants who have < T-VASI25 will receive combination therapy of ruxolitinib cream 1.5% BID in combination with NB-UVB phototherapy 3 times per week through Week 48. Participants who have  $\geq$  T-VASI25 at Week 12 will continue to receive ruxolitinib cream monotherapy. This combination regimen should provide adequate stimulation to the melanocytes to augment the repigmentation provided by ruxolitinib cream alone.

#### 2.7. Benefit/Risk Assessment

Results from dermal safety studies to evaluate local tolerability in healthy participants demonstrate that ruxolitinib 1.5% cream did not cause sensitization and was only slightly irritating under exaggerated testing conditions (occlusive application). In addition, ruxolitinib 1.5% cream was not phototoxic and did not induce photosensitization. This was further confirmed by the available safety data in the Phase 2 and Phase 3 studies where ruxolitinib cream was well tolerated at the application sites with infrequently reported application site reactions.

In participants with vitiligo, all ruxolitinib treatment strengths were generally safe and well tolerated with no significant TEAEs or application site events. The TEAE rate overall was low and similar between active treatment and vehicle. Application site acne was noted as an adverse drug reaction in the IB. The rate of TEAEs leading to discontinuation from treatment was low. No serious TEAE had a fatal outcome nor were they considered related to the study cream by the investigator. There were no clinically meaningful changes in chemistry or hematology parameters, and no clinically meaningful changes were noted for vital signs.

A comprehensive analysis of potential safety concerns associated with oral ruxolitinib and other oral JAK inhibitors was performed. As expected given the low bioavailability and the low plasma concentrations of ruxolitinib observed following topical application, ruxolitinib cream was not associated with these safety concerns.

Narrow-band UVB is generally safe and there were no safety issues with the combination in the small subset of participants in Study INCB 18424-211. There are no substantial safety issues expected.

Ruxolitinib cream showed statistically significant and clinically meaningful improvement in participants with vitiligo compared with vehicle. Also, among the 19 participants who received combination therapy with ruxolitinib 1.5% cream and NB-UVB in Study INCB 18424-211, F-VASI and T-VASI improvements after add-on phototherapy increased for all response parameters.

As ruxolitinib 1.5% cream is generally safe and well tolerated and showed clear benefit in the Phase 2 and Phase 3 studies, the benefit risk profile is expected to be positive.

More detailed information about the known and expected benefits and risks and reasonably expected adverse events of ruxolitinib cream may be found in the IB.

### 3. OBJECTIVES AND ENDPOINTS

Table 5 presents the objectives and endpoints.

**Table 5:** Objectives and Endpoints

Objectives	Endpoints
Primary	
To evaluate the efficacy of ruxolitinib cream in combination with NB-UVB in participants with vitiligo.	Change from baseline in T-VASI at Week 48.
Secondary	
To evaluate the safety and tolerability of ruxolitinib cream in combination with NB-UVB.	Occurrence of AEs and evaluation of vital signs and laboratory data.
To further evaluate the efficacy of ruxolitinib cream in combination with NB-UVB in participants with vitiligo.	
 
Proportion of participants achieving F-VASI50/75/90 at each postbaseline visit.
 
Proportion of participants achieving T-VASI50/75/90 at each postbaseline visit.
 
Change and percentage change from baseline in F-VASI/T-VASI at each postbaseline visit.
 
Change and percentage change from baseline in F-BSA/T-BSA at each postbaseline visit.
 

To evaluate the ruxolitinib PK in plasma after treatment with ruxolitinib cream in combination with NB-UVB.	Population-based (trough) plasma concentrations of ruxolitinib at Weeks 4, 12, and 16.

**Table 5:** Objectives and Endpoints (Continued)

#### 4. STUDY DESIGN

### 4.1. Overall Design

This is an open-label study in which participants will apply ruxolitinib 1.5% cream BID to all depigmented areas up to 10% BSA for up to 48 weeks. Participants should continue to treat depigmented areas identified for treatment at baseline regardless of whether the area begins to improve or fully repigment.

On Day 1, all participants will apply ruxolitinib 1.5% cream BID as monotherapy (see Figure 1). At Week 12, participants will apply ruxolitinib 1.5% cream alone or in combination with NB-UVB based on improvement in T-VASI score. Participants who have < T-VASI25 will have NB-UVB phototherapy added to their ruxolitinib 1.5% cream BID regimen (Group A). NB-UVB will be given 3 times per week through Week 48 (36 weeks). Participants who have  $\geq$  T-VASI25 at Week 12 will continue on ruxolitinib 1.5% cream BID alone (Group B). For participants who receive combination therapy, NB-UVB machines will be supplied by the sponsor for at home use during the study.

At any time during the study, if vitiligo areas become significantly more extensive than from the previous visit, the participant should contact the study site to discuss with the investigator whether additional evaluation at the clinic is required. Participants who have expansion of areas of vitiligo identified at baseline or new areas of vitiligo during the course of the treatment period should not treat the additional areas of vitiligo with ruxolitinib cream.

Participants who permanently discontinue NB-UVB will be allowed to remain in the study and continue to apply ruxolitinib 1.5% cream BID alone. Participants who permanently discontinue ruxolitinib 1.5% cream BID will be allowed to remain in the study and continue NB-UVB phototherapy alone.

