#### **8.3.1.** Adverse Events

Adverse events will be monitored from the time the participant signs the ICF until at least 30 days after the last application of study cream. Adverse events for enrolled participants that begin or worsen after informed consent should be recorded on the Adverse Event Form in the eCRF regardless of the assumption of a causal relationship with the study cream. Conditions that were already present at the time of informed consent should be recorded on the Medical History Form in the eCRF. Adverse events (including laboratory abnormalities that constitute AEs) should be described using a diagnosis whenever possible rather than by individual underlying signs and symptoms.

Adverse events will be reported by the participant (or, when appropriate, by a caregiver, surrogate, or the participant's legally authorized representative). The investigator and any qualified designees are responsible for detecting, documenting, and recording events that meet the definition of an AE or SAE and remain responsible for following up on AEs that are serious, considered related to the study cream/procedures, or that caused the participant to discontinue the study cream or NB-UVB. Care will be taken not to introduce bias when detecting AEs and/or SAEs. Open ended and nonleading verbal questioning of the participant, such as "How are you feeling?", is the preferred method to inquire about AE occurrences. Adverse events may also be detected when they are volunteered by the participant during the screening process or between visits or through physical examinations, laboratory tests, or other assessments. The definition, reporting, and recording requirements for AEs are described in Section 9.

All SAEs will be reported to the sponsor or designee within 24 hours. The investigator will submit any updated SAE data to the sponsor within 24 hours of it being available.

After the initial AE/SAE report, the investigator is required to proactively follow each participant at subsequent visits/contacts. All SAEs will be followed until resolution, stabilization, the event is otherwise explained, or the participant is lost to follow-up (as defined in Section 7.3).

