## 8.7. End of Treatment and/or Early Termination

If a decision is made that the participant will permanently discontinue application of study cream, the EOT visit should be conducted. If the EOT visit coincides with a regular study visit, then the EOT evaluations will supersede those of that scheduled visit, and the data should be entered in the EOT page in the eCRF. If this decision does not coincide with a regular visit, reasonable efforts should be made to have the participant return to the site to have the EOT procedures completed.

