# 8.8. Safety Follow-Up

The safety follow-up period is the interval between the EOT visit and the scheduled safety follow-up visit, which should occur 30 (+7) days after the EOT visit (or after the last application of study cream if an EOT visit was not performed).

Adverse events and SAEs must be reported up until at least 30 days after the last application of study cream/treatment. Adverse events and SAEs must be followed until toxicities resolve, return to baseline, or are deemed irreversible. Reasonable efforts should be made to have the participant return for the safety follow-up visit and report any AEs that may occur during this period.

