## 9.4. Reporting of Serious Adverse Events

Regardless of suspected causality (eg, relationship to study cream, study procedures), all SAEs occurring after the participant has signed the ICF through the last safety visit or at least 30 days after the last application of study cream must be reported to the sponsor (or designee) immediately, without undue delay, but not later than within **24 hours** of obtaining knowledge of its occurrence unless otherwise specified by the Protocol. The investigator will submit any updated SAE data to the sponsor (or designee) immediately, without undue delay, but not later than within 24 hours of it being available.

Investigators are not obligated to actively seek SAE information after the safety follow-up visit or 30 days after the last application of study cream. If the investigator learns of any SAE, including death, at any time during this period, and the event is considered to be reasonably related to the study cream or study participation, the investigator must notify the sponsor (or designee) within 24 hours of becoming aware of the event.

After the initial AE/SAE report, the investigator is required to proactively follow each participant at subsequent visits/contacts. All SAEs will be followed until resolution, stabilization, the event is otherwise explained, or the participant is lost to follow-up (as defined in Section 7.3).

Prompt notification by the investigator to the sponsor regarding an SAE is essential so that legal obligations and ethical responsibilities toward the safety of participants and the safety of a study cream under clinical investigation are met.

If the SAE is not documented in the RSI of the IB for the study cream (new occurrence) and is thought to be related to the study cream, the sponsor or its designee may urgently require further information from the investigator for expedited reporting to health authorities. The sponsor or its

designee may need to issue an Investigator Notification to inform all investigators involved in any study with the same drug that this SAE has been reported. Suspected unexpected serious adverse reactions will be collected and reported to the competent authorities and relevant ethics committees in accordance with Directive 2001/20/EC or as per national regulatory requirements in participating countries.

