9.2. Adverse Events

9.2.1. Adverse Event Definitions

A TEAE is any AE either reported for the first time or worsening of a pre-existing event after first application of study drug and within 30 days of the last application of study drug. For participants who have NB-UVB phototherapy added, the first application date is period-specific, and the end date is 30 days after the last application date in this period, or the day before the first application date in the next period, whichever comes first. Analysis of AEs (as discussed below) will be limited to TEAEs, but data listings will include all AEs regardless of their timing in relation to study drug application.

Adverse events will be tabulated by MedDRA PT and SOC. Severity of AEs will be graded using the NCI CTCAE v5. The CTCAE reporting guidelines and grading details are available on the Cancer Therapy Evaluation Program website.

The subset of AEs considered by the investigator to be related to study drug will be considered to be treatment-related AEs. If the investigator does not specify the relationship of the AE to study drug, the AE will be considered to be treatment-related. The incidence of AEs and treatment-related AEs will be tabulated. Serious AEs will also be tabulated.

Any missing onset date, causality, or severity must be queried for resolution. Unresolved missing causality and severity will be handled according to the following rules:

- An unresolved missing causality will be considered treatment-related.
- An unresolved missing severity will be identified as an unknown severity.

For purposes of analysis, all AEs will be considered TEAEs unless the AE can unequivocally be defined as not treatment-emergent.

Application site reactions are AEs that occur at the site of drug application. A summary of ASRs will be provided.

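### The SAP's treatment-emergent window appears to end 30 days after the last cream application, although participants may stop the cream and continue NB-UVB; the Protocol's safety-collection rules for that state conflict.

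*Protocol*

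**What the plan says.** Group A starts home phototherapy at Week 12: "NB-UVB will be given 3 times per week through Week 48 (36 weeks"). Protocol 4.1 then provides for a participant who gives up the cream only: "Participants who permanently discontinue ruxolitinib 1.5% cream BID will be allowed to remain in the study and continue NB-UVB phototherapy alone".

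The rules that key on the cream are:
- **End of treatment (Protocol 7.1.2 and 8.7):** "If a decision is made that the participant will permanently discontinue application of study cream, the EOT visit should be conducted".
- **Safety follow-up visit (Protocol 8.8):** "which should occur 30 (+7) days after the EOT visit". Table 4 labels this visit end of study.
- **AE monitoring (Protocol 8.3.1):** "until at least 30 days after the last application of study cream".
- **Serious AE reporting (Protocol 9.4):** "through the last safety visit or at least 30 days after the last application of study cream".
- **Concomitant medication (Protocol 6.6):** recorded to 30 days after the last cream application, with an extension for treatment of a serious AE.
- **Treatment-emergent AEs (SAP 9.2.1):** events arising or worsening "after first application of study drug and within 30 days of the last application of study drug".

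The wider text is:
- **Protocol 8.8:** "Adverse events and SAEs must be reported up until at least 30 days after the last application of study cream/treatment". Section 6.1 lists NB-UVB among the study treatments (Table 7).
- **Tables 2 and 4:** safety follow-up may be counted from the last visit as an alternative to the last application.
- **Protocol 8.3.5:** the duty to repeat clinically significant abnormal laboratory tests covers anyone still participating, as well as the 30 days after the cream.
- **Protocol 10.4.2, Table 15:** the treatment-emergent definition has a start but no end.
- **Table 4:** AE assessment at every visit from Week 16 to Week 48.

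**The concern.** The plan permits a treatment state, NB-UVB alone, for which it gives no safety rules. A site that follows 7.1.2, 8.7 and 8.8 literally would hold the visit labelled end of study about 30 days after the cream stops, while the participant may still be using the device at home. A site that follows Table 4 would keep assessing AEs to Week 48. Both can claim to be following the Protocol, so collection could differ between sites.

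Whatever is collected then meets the SAP window. Safety and tolerability of the cream combined with NB-UVB is a secondary objective, and the AE analyses are limited to treatment-emergent events. The Protocol itself recognises phototherapy reactions: skin burning in 9.10, and painful erythema in 6.5.3. A reaction of this kind late in the course could be recorded and still be absent from every AE table.

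**Working it through.** **1. Phototherapy course.** Week 12 to Week 48 is 48 − 12 = 36 weeks, which reproduces the figure in Protocol 4.1. That is 36 × 7 = 252 days, or 36 × 3 = 108 planned sessions.

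**2. Time outside a cream-anchored window.** If the cream stops at Week s, phototherapy has run for 7(s − 12) days and the window stays open for 30 more. With NB-UVB continuing to Week 48:

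days outside = max(0, 252 − 7(s − 12) − 30)

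| Cream stops | Calculation | Days outside | Share of 252 days |
|---|---|---|---|
| Week 16 | 252 − 28 − 30 | 194 | 77% |
| Week 24 | 252 − 84 − 30 | 138 | 55% |
| Week 32 | 252 − 140 − 30 | 82 | 33% |
| Week 40 | 252 − 196 − 30 | 26 | 10% |

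The result reaches zero at s = 48 − 30/7, about Week 43.7. More than half of the course (126 days) lies outside only if 7(s − 12) < 252 − 30 − 126 = 96, that is, if the cream stops before about Week 25.7.

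**3. Does study drug mean the cream in the SAP?** SAP 6.5, headed as study drug compliance, computes compliance for the cream only. NB-UVB has its own section, 6.6. SAP 4.1.1 defines Day 1 by application of the cream. SAP 9.2.1 adds a period-specific rule for participants given NB-UVB, but that rule still counts from the last application date in the period and does not say whether a phototherapy session is an application. The cream reading is the more natural one, but it is not stated.

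**4. Does the SAP's default rescue these events?** SAP 9.2.1 counts an AE as treatment-emergent unless it unequivocally is not. On the cream reading, take an event at Week 40 in a participant who stopped the cream at Week 16. Its onset is 24 × 7 = 168 days after the last application, and with a known onset date it is unequivocally outside a 30-day window. The default does not apply.

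**5. SAP against Protocol.** Table 15 sets no end to the treatment-emergent period and the SAP sets one, yet SAP 11.1 records no change to the Protocol-defined analyses.

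**The case against.** The strongest reply is that much of the Protocol is wider than the cream. Section 8.8 refers to treatment as well as cream, Tables 2 and 4 allow the last visit as an anchor, the limits in 8.3.1, 8.8 and 9.4 are worded as minimums, and Table 4 schedules AE assessment throughout. Section 4.1 keeps these participants in the study. This stands. A reader might infer that every safety window closes with the cream and that later AEs go uncollected. The documents do not support that: they conflict, and collection is uncertain rather than shut.

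A second reply is that the SAP means to capture phototherapy events. The Appendix A note on Cohort A refers to events related to either treatment, and listings include all AEs whatever their timing. The intent is plausible. But the Cohort A table is itself restricted to treatment-emergent events, so the window still governs it, and a listing does not enter a rate.

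A third reply is that the objective concerns the combination and SAP 5.2 summarises by treatment received, so events long after the last cream application belong to NB-UVB alone. This also stands, and it is why such events should be identifiable rather than merged. It also weakens the inference that Group A rates are biased downward. That would require later events to occur, to belong to the combination estimate, and to fall in participants not already counted in the same table row.

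Finally, the affected group may be very small or empty. Protocol 2.7 describes discontinuation for AEs as low, and 6.5.1 asks investigators to consider interrupting both treatments when the cause of a skin reaction is unclear.

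**Conclusion.** The SAP window is wrong as written for participants who continue NB-UVB after stopping the cream. If study drug means the cream, their AEs that start more than 30 days after the last application are left out of all treatment-emergent summaries. The time affected depends on when the cream stops: from 77% of the phototherapy course at Week 16 down to 10% at Week 40 and nothing from about Week 43.7. It would be too strong to say that most of the phototherapy falls outside in general, because for the whole course that holds only for stops before about Week 25.7.

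These figures assume NB-UVB to Week 48 and exactly 30 days of cover after the cream. The documents give no expected number of such participants, so no effect on event rates can be estimated. On the collection side, the conclusion is limited to conflicting Protocol text that needs reconciling.

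**What to change.** 1. **SAP 9.2.1.** For participants with NB-UVB added, end the treatment-emergent window 30 days after the later of the last cream application or the last NB-UVB session. Show events that start on NB-UVB alone, more than 30 days after the last cream application, as a separate row or flag. Record the difference from the Protocol's treatment-emergent definition in SAP 11.1.
2. **Protocol 6.6, 8.3.1, 8.8 and 9.4.** Use the same later-of-two anchor for AE, serious AE and concomitant medication collection.
3. **Protocol 4.1, Tables 2 and 4, 7.1.2, 8.7 and 8.8.** Reconcile these so that the assessments triggered when the cream stops are kept, but the 30-day safety follow-up (end-of-study) visit is not completed while NB-UVB continues. State that these participants stay on the Table 4 visits, which the documents do not now say.

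The cost is wording changes and a programming rule with a flag. The downside is somewhat longer AE collection for these participants and possibly slightly higher reported AE counts.

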### 4.2. Overall Study Duration

The study begins when the first participant signs the study ICF. It is estimated that an individual will participate for approximately 14 months (up to 30 days for screening, up to 48 weeks of treatment, and 30 days for safety follow-up).

A participant is considered to have completed the study if they have completed the 48-week treatment period and the safety-follow-up period. A study is considered completed when the last participant last visit has occurred.

